7.1. General Considerations

Unless otherwise noted, all tests of treatment effects will be conducted at a 2-sided alpha level of 0.05; 2-sided confidence intervals will be displayed with a 95% confidence level. All tests of interactions between treatment and other factors will be conducted at an alpha level of 0.05.

All analyses will follow the modified intent-to-treat (mITT) principle unless otherwise specified. An ITT analysis is an analysis of data by groups to which the participants are assigned by random allocation, even if the participant does not take the assigned treatment, does not receive the correct treatment, or otherwise does not follow the protocol. An mITT analysis is an ITT analysis for all participants who have a baseline and at least 1 postbaseline measure. All safety analyses will be done using the safety population. Analysis populations are described below (Section 7.5).

When change from baseline is assessed, participants will be included in the analysis only if both a baseline and a post-baseline measure are available. Unless otherwise defined, a baseline measure is the last non-missing observation collected prior to the first infusion of study medication. End point is the last non-missing post-baseline measurement.

For MMRM analyses, observations collected at non-scheduled visits (see Section 7.2) will not be included in the analyses. For NCS and MMRM analyses, unless otherwise specified, an unstructured covariance structure will be used. If the unstructured covariance structure matrix results in a lack of convergence, the following covariance structures will be used in sequence: heterogeneous Toeplitz covariance structure, heterogeneous autoregressive covariance structure, heterogeneous compound symmetry covariance structure and homogeneous compound symmetry covariance structure.

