7.4. Multiple Comparisons/Multiplicity

The primary analysis is the NCS analysis of the PACC (Section 7.9.1). All other analyses are secondary to this analysis.

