7.9.1.2.4. Assessing Effect of Exposure

Additionally, we will implement a sensitivity analysis to estimate the potential differences in the cumulative treatment exposure over time due to both the dose increase and the COVID-19 hiatus. In addition to the two spline basis expansion terms for time from baseline in the primary analysis NCS model, this model will also include spline basis expansion terms for the cumulative exposure to solanezumab over time. The fixed effects will include the following terms: (i) NCS basis expansion terms for time (two terms), (ii) NCS basis expansion terms for cumulative exposure (two terms), (iii) PACC test version administered, (iv) age, (v) education, (vi) APOE4 Carrier Status (yes/no), and (vii) baseline florbetapir cortical SUVr. Treatment group is not explicitly included in the model, but the cumulative exposure for the placebo group is set to zero. Based on this model, we will be able to visualize the modeled mean for the PACC over time with 95% confidence intervals for (i) placebo group, (ii) the low-dose per-protocol exposure, and (iii) the high-dose per-protocol exposure. We will also be able to visualize the modelled mean PACC at 240 weeks for the observed range of cumulative dose exposure and identify the minimum exposure at which the 95% confidence interval excludes the mean for the placebo group.

To further investigate exposure, participants will be grouped into one of three exposure groups based on the tertiles of the distribution of cumulative exposure to either solanezumab or placebo: low exposure, medium exposure, and high exposure. Within these exposure groups, solanezumab-treated participants will be compared to placebo-treated participants using the NCS model including effects for (i) NCS basis expansion terms, (ii) exposure group (iii) NCS basis expansion terms-by-treatment-by-exposure group interaction, (iv) PACC test version administered, (v) age, (vi) education, (vii) APOE4 Carrier Status (yes/no), and (viii) baseline florbetapir cortical SUVr. This model will constrain the baseline treatment group means to be the same within exposure group, but allow different baseline means between the exposure groups. The interaction will be tested by likelihood ratio test comparing the full model to the reduced model without any exposure group interaction effects.

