7.9.2.2. CDR Global Score

Participants will be classified for clinical worsening based on the CDR Global Score. As all participants begin the trial with a CDR Global Score of 0, clinical worsening will be defined as two consecutive CDR Global Scores above 0, or an endpoint CDR Global Score above 0.

Association between treatment and clinical worsening at any time during the double-blind treatment phase will be tested using Fisher's Exact test.

Time to clinical worsening will be assessed through a Kaplan-Meier analysis. For participants who meet the definition of clinical worsening, time to clinical worsening will be defined as the time from randomization to the first non-zero assessment of the CDR Global Score that contributes to the clinical worsening. Participants who do not meet the definition of clinical worsening will be censored at the time of their last CDR Global Score assessment. Treatments will be compared using the log-rank test.

Additionally, time to clinical worsening will also be measured with a Cox proportional hazards model. Definitions of time to event will be identical to those used for the Kaplan-Meier analyses. Time to clinical worsening will be modelled with fixed effects for baseline PACC score, treatment, age, education, APOE4 Carrier Status (yes/no), and baseline florbetapir cortical SUVr. The coefficient associated with treatment will be tested using the Wald Chi-squared statistic.

For both the Kaplan-Meier and the Cox proportional hazard models, APOE4 Carrier Status (yes/no) will also be investigated for differences in time to clinical worsening.

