7.15. Subgroup Analyses

To assess the effects of various demographic and baseline characteristics on treatment outcome, subgroup analyses for the primary endpoint, PACC, will be performed based on the following variables:

- Gender: Male/Female
- Age: ≥ 65 years and < 75 years, ≥ 75 years and < 85 years
- Race: Dichotomized based on distribution of race at baseline.
- APOE4 Carrier Status: Carrier defined as $\epsilon 2/\epsilon 4$, $\epsilon 3/\epsilon 4$, or $\epsilon 4/\epsilon 4$ genotype; Non-Carrier defined as all other genotypes.
- APOE4 Genotype: $\epsilon 2/\epsilon 4$, $\epsilon 3/\epsilon 4$, $\epsilon 4/\epsilon 4$, No $\epsilon 4$
- Family History of AD: Yes/No
- Reason for Discontinuation: Categories as defined by the subject disposition case report form. Due to sparseness within certain categories, categories may be collapsed after seeing the actual distributions.

The primary outcome measures will be modeled using an NCS approach. This general model will include effects for (i) NCS basis expansion terms, (ii) subgroup (iii) NCS basis expansion terms-by-treatment-by-subgroup interaction, (iv) PACC test version administered, (v) age, (vi) education, (vii) APOE4 Carrier Status (yes/no), and (viii) baseline florbetapir cortical SUVr. This model will constrain the baseline treatment group means to be the same within subgroup levels, but allow different baseline means for the subgroups. Redundant terms will be dropped from the model in those cases in which the subgroup of interest is overlapping with this general model. The interaction will be tested by likelihood ratio test comparing the full model to the reduced model without any subgroup interaction effects.

To evaluate dose effect on the primary outcome measure, marginal structural models, inverse probability of treatment weighting (MSM, IPTW) methodology will be used (Lipkovich et al, 2008). Dose profiles for mean changes from baseline will be evaluated using weighted MSM with a repeated measures model. To adjust for selection bias due to non-random dose assignment and dropouts, participant-specific time-dependent weights will be determined as products of (i) stable weights based on inverse probability of receiving the sequence of dose assignments that was actually received by a participant up to given time multiplied by (ii) stable weights based on inverse probability of participant remaining on treatment by that time.

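### The subgroup interaction test in SAP 7.15 also rejects when a subgroup simply declines faster in both arms, so its nominal 5% level does not hold as a test of treatment interaction

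*SAP*

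**What the plan says.** SAP 7.15 lists the terms of the subgroup model as "i) NCS basis expansion terms, (ii) subgroup (iii) NCS basis expansion terms-by-treatment-by-subgroup interaction", followed by PACC version, age, education, APOE4 carrier status and baseline SUVr. Treatment means at baseline are held equal within each subgroup level, and the model will "allow different baseline means for the subgroups". The test is then defined: "The interaction will be tested by likelihood ratio test comparing the full model to the reduced model without any subgroup interaction effects".

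No spline-by-subgroup term is listed. The covariates enter as main effects and are not crossed with time. The SAP does not say how treatment is coded in the three-way term.

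SAP 7.1 sets the level: "All tests of interactions between treatment and other factors will be conducted at an alpha level of 0.05". SAP 7.4 names the NCS analysis of the PACC as primary and adds: "All other analyses are secondary to this analysis".

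SAP 7.9.1.2.4 repeats the construction for exposure groups formed "based on the tertiles of the distribution of cumulative exposure to either solanezumab or placebo": "The interaction will be tested by likelihood ratio test comparing the full model to the reduced model without any exposure group interaction effects".

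**The concern.** A test of treatment interaction should ask whether the treatment effect differs between subgroups. It should not react when one subgroup has a worse prognosis in both arms. Here the reduced model has no term for a different rate of decline by subgroup, so any such difference becomes lack of fit that only the full model can absorb. The consequence depends on the coding.

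- **(a) Treatment as an ordinary factor.** Each treatment-by-subgroup cell gets its own curve. The likelihood ratio then tests different decline and different treatment effect together. The subgroup treatment estimates stay valid, but the p-value does not answer the intended question.
- **(b) Treatment as an active-arm indicator.** The placebo curve is common to all subgroups. The active-arm terms absorb the difference in decline, so the subgroup treatment estimates are biased as well.

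Several of the 7.15 factors could plausibly relate to rate of decline. The SAP itself plans to look at this for one of them in 7.9.2.2: "APOE4 Carrier Status (yes/no) will also be investigated for differences in time to clinical worsening". What is at stake is a report that solanezumab works differently in, say, APOE4 carriers, when the data show only that carriers decline at a different rate in both arms.

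**Working it through.** **Inputs from the documents.** N = 1150, 1:1 (SAP 6.1, 6.3); 30% attrition, taken here as linear over time; SD of PACC change 2.85 (ADNI) or 3.08 (HABS) at week 240 and 3.77 or 3.99 at week 336; visit-to-visit correlation about 0.5 (SAP 6.2); PACC every 24 weeks from 0 to 240, so 11 visits (Protocol Attachment 1); spline with 2 df (SAP 7.9.1.1); level 0.05 (SAP 7.1).

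**Assumptions.** A two-level subgroup with a share of 30–70%; knots at 0, 120 and 240 weeks; extra decline D, linear in time, reached at week 240 in one subgroup and equal in both arms; no treatment effect in any subgroup. Five covariances:

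- Two random-slope models. The slope variance is (3.77² − 2.85²)/(336² − 240²) = 6.0904/55296 per week². At week 240 this contributes 6.0904 × 57600/55296 = 6.34 of the total 2.85² = 8.12, leaving (8.12 − 6.34)/2 = 0.89 residual variance per visit. The HABS figures give 6.70 and 1.39 in the same way.
- Two compound-symmetry models with correlation 0.5 and change SD 2.85 or 3.08.
- One heterogeneous compound-symmetry model with correlation 0.5.

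**Counting parameters for two levels** (PACC version and the other covariates left out).

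| Model | Terms | Rank |
|---|---|---|
| Reduced, as written | intercept 1, subgroup 1, spline 2, spline × treatment 2 | 6 |
| Full (a) | intercept 1, subgroup 1, four cell curves × 2 | 10 |
| Full (b) | intercept 1, subgroup 1, spline 2, active-arm curve per level 2 × 2 | 8 |
| Corrected reduced | as the reduced model, plus spline × subgroup 2 | 8 |
| Corrected full | four cell curves, as full (a) | 10 |

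The test as written has 10 − 6 = 4 df under (a), of which 2 are purely prognostic, or 8 − 6 = 2 df under (b). The corrected test has 10 − 8 = 2 df.

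**Formula.** For each model M, let Q(M) be the smallest value over β of Σ n_c(μ_c − X_cβ)′V⁻¹(μ_c − X_cβ), summed over cells and dropout patterns. The noncentrality is λ = Q(reduced) − Q(full), and the rejection rate is P(χ²_df(λ) > χ²_df,0.95).

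**Stated level first.** With D = 0, λ = 0 and all versions give 5.0%, as the SAP intends.

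**One case in full.** Take a random-intercept-and-slope covariance with change SD 2.85, residual variance 1.5, a 50% share, 30% attrition and D = 0.5. Under (a), λ = 9.17 against a critical value of 9.49, giving 67%. Under (b), λ = 4.55 against 5.99, giving 47%. In the corrected test λ = 0, giving 5.0%.

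**Range over the five covariances and shares of 30–70%, 30% attrition.**

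| D at week 240 | (a), 4 df | (b), 2 df | Corrected, 2 df |
|---|---|---|---|
| 0 | 5% | 5% | 5% |
| 0.25 | 14–30% | 11–21% | 5% |
| 0.5 | 50–90% | 34–68% | 5% |
| 1.0 | ≥99% | 90–100% | 5% |

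Without attrition the rates at D = 0.5 are 58–96% (a) and 39–79% (b). The level reaches 10% at D = 0.12–0.19 (a) or 0.15–0.22 (b). For scale only, 0.12/2.13 ≈ 6% and 0.22/2.13 ≈ 10% of the 2.13-point amyloid-group difference in SAP 6.2.

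**Four-level genotype, D = 0.5.** With assumed shares (no ε4, ε2/ε4, ε3/ε4, ε4/ε4) of 50/5/38/7% and 40/5/45/10%, rejection is 36–73% (a, 12 df) and 24–49% (b, 6 df).

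**Bias, under (b) only.** At D = 0.5 and a 50% share, the model shows a false week-240 effect of about −0.23 to −0.25 points in the faster-declining subgroup and +0.23 to +0.25 in the other.

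**Simulation with estimated unstructured covariance (ML).** ADNI random-slope model, 50% share, no attrition, 2000 trials per setting. At D = 0/0.25/0.5/1.0 the test rejects in 5.5/21.4/71.8/100% (a) and 5.1/16.9/50.8/97.9% (b), and the corrected test in 5.6/4.7/4.4/5.1%. A separate run used 805 completers (1150 × 0.7), the residual-variance-1.5 covariance and 1000 trials. At D = 0.5 it gives 58% (a), 40% (b) and 5.3% (corrected).

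**The case against.** The strongest reply is that the only interaction 7.15 lists is the three-way term. On that view its removal means dropping treatment-by-subgroup effects only, with spline-by-subgroup terms understood in both models. That test would be valid. But no such term is listed, the reduced model excludes every subgroup interaction, and 7.9.1.2.4 has the same wording. At best the plan is under-specified on the point that decides validity.

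Four further objections have force:

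- **Size is assumed.** The plan for APOE4 in 7.9.2.2 is an intention to look, not evidence. Protocol Attachment 3 uses APOE ε4 as a stand-in where amyloid was not measured, whereas every A4 participant is amyloid-positive. The 2.13-point yardstick contrasts amyloid-positive with amyloid-negative people, a contrast this trial does not contain.
- **The upper ends come from compound symmetry**, which holds the SD of change constant although the documents have it rising from 2.85 to 3.77. The two random-slope models with 30–50% shares and 30% attrition give 14–18% at 0.25 points and 50–64% at 0.5 points under (a), and 11–14% and 34–44% under (b). These are the better central figures, and they are still far above 5%.
- **Reading (b) is the less likely one.** R fits with treatment and subgroup as factors would normally give each cell its own curve. The bias claim therefore stays conditional on (b).
- **These analyses are secondary**, with no multiplicity control, so they could not carry a confirmatory claim. That limits the consequence but does not make the p-value mean what its label says.

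**Conclusion.** The concern holds: as written, the 7.15 test is not a 5% test of treatment-by-subgroup interaction unless the subgroups decline in parallel. That conclusion follows from the listed terms and needs no numerical assumption. The amount of inflation does depend on assumptions: the gap in decline, the subgroup share, the covariance and a linear divergence. At 0.5 points the 5% test rejects in 50–90% of trials under factor coding and 34–68% under indicator coding, with the random-slope models at the lower end. Under factor coding only the p-value is wrong. Under indicator coding the subgroup treatment estimates are biased too.

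The test in 7.9.1.2.4 has the same fault, and its groups are also formed after randomisation. The primary PACC test is untouched. This should be corrected before the subgroup p-values are reported, but it does not threaten the main conclusion.

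Two smaller points in the same section also need correction. Reason for discontinuation is a post-randomisation variable in a section meant for demographic and baseline characteristics. The upper age band stops below 85, here and in SAP 7.13.1.2, although Protocol 8.1 admits 85-year-olds.

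**What to change.** In SAP 7.15, write out both models and state the treatment coding.

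- **Reduced:** spline, subgroup, spline-by-treatment, spline-by-subgroup, plus the covariates.
- **Full:** the same plus spline-by-treatment-by-subgroup.

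Fit both by maximum likelihood and test only the three-way terms, with 2(k − 1) df for k levels: 2 df for two levels and 6 df for the four-level genotype. The spline-by-subgroup terms must be in both models. Under indicator coding, adding them to the reduced model alone would leave the two models non-nested.

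Use the same pair in 7.9.1.2.4, but label the exposure-tertile comparison descriptive, because the added terms do not remove selection on a post-randomisation variable. Report reason for discontinuation descriptively for the same reason. Define the upper age band as 75 and over in 7.15 and 7.13.1.2.

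The cost is SAP wording and 2(k − 1) extra parameters in the reduced model. There is also a loss of power if the subgroups truly decline alike. For an assumed 1.0-point interaction with 30% attrition and a 50% share, power is 70–98%, against 90–100% for the test as written under (a). At a 30% share with the random-slope models it is 62–67% against 83–88%. The higher figures belong to a test that holds its level only when decline is parallel.

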7.16. Protocol Violations

Listings of participants with significant protocol violations will be provided for the ITT population. The following list of significant protocol violations will be determined from the clinical database and from the Lilly/ATRI clinical/medical group.

- Informed consent violation.

- Did not have an assessment of PACC at any of the visits at which the scale was scheduled to be assessed.
- Protocol violations of inclusion/exclusion criteria.
- Had a study dosing algorithm violation (such as if participants randomized to treatment A were given treatment B or participants randomized to treatment A never received the assigned study drug.)
- Had unqualified raters or raters with substantial scoring errors for the PACC.
- Greater than or equal to 20% of infusions are incomplete.
- One or more missed infusions.
- Violated the protocol in any other way.

7.17. Interim Analyses and Data Monitoring

The ATRI-Coordinating Center (ATRI-CC) currently has a Data Safety Monitoring Board (DSMB) that reviews the safety of all subjects enrolled in trials on an ongoing basis. The initial task of the DSMB will be to review the protocol and consent forms to identify any necessary modifications. If modifications are necessary, revisions will be reviewed by the DSMB prior to its recommendation on initiation of the project. The DSMB, based on its review of the protocol, will identify the data parameters and format of the information to be regularly reported. The DSMB will be informed of the occurrence of any SAEs and immediately notified of fatal or life-threatening events. The DSMB may at any time request additional information from the ATRI-CC. The DSMB will initially be provided with data blinded to treatment status, but they may request unblinded data if there is a safety concern. The DSMB and National Institute on Aging (NIA) representative will meet in person or by conference call on a quarterly basis. Based on the review of safety data, the DSMB will make recommendations regarding the conduct of the study. These may include amending safety monitoring procedures, modifying the protocol or consent, terminating the study or continuing the study as designed. The DSMB will also be informed in a real-time basis of all immediately reportable AEs (FDA-defined serious AE). All reports are stripped of identifying information. Using the ATRI safety review process and the DSMB, there is substantial oversight and case review to alert the investigators, in a timely manner, to any safety issues that may arise. For further details, please refer to the DSMB charter.

7.18. Clinical Trial Registry Analyses

Additional analyses will be performed for the purpose of fulfilling the Clinical Trial Registry (CTR) requirements.

Analyses provided for the CTR requirements include the following:

Summary of AEs, provided as a dataset which will be converted to an XML file. Both SAEs and 'Other' AEs are summarized: by treatment group, by MedDRA preferred term.

- An AE is considered ‘serious’ whether or not it is a treatment emergent adverse event (TEAE).
- An adverse event is considered in the ‘Other’ category if it is both a TEAE and is not serious. For each serious AE and ‘Other’ AE, for each term and treatment group, the following are provided:
 - the number of participants at risk of an event
 - the number of participants who experienced each event term, and
 - the number of events experienced.
- Consistent with www.ClinicalTrials.gov requirements, ‘Other’ AEs that occur in fewer than 5% of participants or participants in every treatment group may not be included if a 5% threshold is chosen (5% is the minimum threshold).

8. References

- Hastie TJ. Generalized additive models. In: Chambers JM, Hastie TJ, eds. *Statistical Models in S*. Chapman & Hall/CRC. 1992.

9. Appendices

Appendix 1. List of Florbetapir and Flortaucipir Parameters

The following is the list of brain regions for which florbetapir standardized uptake value ratios (SUVr) will be provided.

1	xlaal_frontal_med_orb ^a
2	new_temporal_2 ^a
3	lprecuneus_gm ^a
4	lnew_parietal ^a
5	llposterior_cingulate_2 ^a
6	lanterior_cingulate_2 ^a
7	blcere_all
8	Composite_Summary

^a Regions used in calculation of the composite summary SUVr.

The following is the list of 8 composite brain regions for which flortaucipir standardized uptake value ratios (SUVr) will be provided.

Basis	Region	Components	N Voxels Left / Right
Staging	Early	MGH-GTM amygdala MGH-GTM entorhinal MGH-GTM parahippocampal	258 / 272 256 / 241 328 / 316
Staging	Middle	MGH-GTM fusiform MGH-GTM inferiortemporal MGH-GTM middletemporal MGH-GTM inferiorparietal	1495 / 1487 1771 / 1715 1737 / 1816 1927 / 2214
Staging	Late	MGH-GTM lateraloccipital MGH-GTM posteriorcingulate MGH-GTM superiorparietal MGH-GTM supramarginal	1622 / 1403 411 / 500 1703 / 1586 1717 / 1614
Staging	Early Extension	MGH-GTM amygdala MGH-GTM entorhinal MGH-GTM parahippocampal MGH-GTM fusiform MGH-GTM inferiortemporal MGH-GTM middletemporal MGH-GTM inferiorparietal	258 / 272 256 / 241 328 / 316 1495 / 1487 1771 / 1715 1737 / 1816 1927 / 2214

Basis	Region	Components	N Voxels Left / Right
Staging	Late Extension	MGH-GTM fusiform MGH-GTM inferiortemporal MGH-GTM middletemporal MGH-GTM inferiorparietal MGH-GTM lateraloccipital MGH-GTM posteriorsingulate MGH-GTM superiorparietal MGH-GTM supramarginal	1495 / 1487 1771 / 1715 1737 / 1816 1927 / 2214 1622 / 1403 411 / 500 1703 / 1586 1717 / 1614
Staging	Combo	MGH-GTM amygdala MGH-GTM entorhinal MGH-GTM parahippocampal MGH-GTM fusiform MGH-GTM inferiortemporal MGH-GTM middletemporal MGH-GTM inferiorparietal MGH-GTM lateraloccipital MGH-GTM posteriorsingulate MGH-GTM superiorparietal MGH-GTM supramarginal	258 / 272 256 / 241 328 / 316 1495 / 1487 1771 / 1715 1737 / 1816 1927 / 2214 1622 / 1403 411 / 500 1703 / 1586 1717 / 1614
Anatomy	Lateral Temporal	MGH-GTM inferiortemporal MGH-GTM middletemporal MGH-GTM superiortemporal MGH-GTM transversetemporal MGH-GTM bankssts	1771 / 1715 1737 / 1816 1774 / 1601 155 / 117 379 / 355
Anatomy	Parietal	MGH-GTM inferiorparietal MGH-GTM superiorparietal MGH-GTM supramarginal MGH-GTM postcentral MGH-GTM precuneus	1927 / 2214 1703 / 1586 1717 / 1614 1268 / 1124 1400 / 1445

